5.1.5.3. Application of Study Drug

Study drug will be dispensed to subjects requiring treatment at the study visits specified in the Schedule of Assessments (

[Table 1](#)).

Subjects will take the tubes home and self-administer (or have a caregiver apply if necessary), except on study visit days (when study drug is applied under supervision at the site), to affected areas once daily.

Subjects will be instructed to apply study drug as follows:

- For subjects with a PGA > 0, once daily application to affected areas including those areas treated in the pivotal study; subjects are to choose the application time they prefer and to apply the study drug at that time each day of study participation.
- Subjects with a PGA of 0 will not receive treatment but if they worsen and experience a PGA of ≥ 2 , apply once daily to newly affected areas only.
- If a subject misses a daily dose, it will be recorded as a protocol deviation. The subject should continue dosing the next day and should not apply more than once daily to make up for the missed dose on the previous day.
- If chosen application time is in the evening, the dose should be applied at least 30 minutes prior to bedtime.
- Study drug should be applied to dry, clean skin
- Wash hands after application, unless treating lesions on the hands or fingernails.
- Study drug should be applied to all lesions, including newly appearing lesions and lesions that have improved during the study.
- Subjects are allowed, but not required, to treat fingernails, toenails, palms, soles, and scalp lesions with study drug; however, efficacy analyses will not include assessment of improvement of psoriasis in these areas). If using study drug on the scalp, no other treatment for scalp psoriasis is permitted during the study.
- If there is residual cream visible on the disease-affected lesional skin, then the subject should be instructed to continue to lightly rub the cream into the skin until it is no longer visible
- If study drug is applied to the subject by another person, that person should thoroughly wash his/her hands after application. When possible, use of disposable gloves is recommended.
- Subjects should record the time of study drug application in the daily diary.
- Subjects should avoid swimming, bathing, showering, or strenuous activities for at least 2 hours after application of study drug.

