7. ANALYSIS POPULATIONS

Intent-To-Treat (ITT) Analysis Set: includes all subjects enrolled into the study. All subjects who signed the informed consent will have enrolled in the study. All efficacy and safety analysis will be performed over ITT analysis set.

Subjects will be analyzed overall and by the original treatment assigned in pivotal studies (DMVT-505-3001 and DMVT-505-3002). This will be referred to below as DB (double-blind) treatment group.

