11.4 Study Medication Exposure and Compliance

Subjects will be characterized by a series of treatment episodes as defined in Section 11.7. These treatment episode definitions are based on attainment of specified PGA values.

The following exposure and compliance parameters will be summarized descriptively over the overall span of treatment episodes, overall and by DB treatment group:

- Total expected number of days exposed, calculated as the sum of number of days over all treatment episodes.
- Total number of doses administered within treatment episodes, calculated from the subject dose diary and summed over all treatment episodes. If a subject does not return diary or returns the diary with missing dosing record, the number of doses taken during that period is assumed to be 0.
- Grams (g) of study drug administered within treatment episodes, total will be summed over all treatment episodes. Drug administered is calculated as the summation of the difference between dispensed weight and returned weight for all returned tubes. Unreturned tubes will be assumed unused and will be included as 0 gram in amount drug used calculation. Average grams of study drug administered per expected day exposed and per doses administered will be calculated as the total grams / total number of days exposure (or total number of doses administered). Subjects with more than 1-day exposure but had no diaries returned will not have average grams per doses administered reported.
- Percent compliance will be calculated as the total number of doses administered within treatment episodes over the total expected number of days exposed.
- Subject compliance, defined as $\geq 80\%$ compliance over the entire duration of study. If the percentage of study medication compliance is unknown, the subject is assumed to be non-compliant with study medication.

In addition, the following exposure parameters will be summarized descriptively for the entire study (regardless of PGA status) overall and by DB treatment group:

- Total number of doses administered, calculated from the subject dose diary and in-clinic dosing. If a subject does not return diary or returns the diary with missing dosing record, the number of doses taken during that period is assumed to be 0.

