11.7 Efficacy Endpoints

Efficacy endpoints are as follows:

For subjects entering the study with a PGA score of clear (0):

- Proportion of subjects who experience PGA ≥ 2 at least 1 time during the study.
- Proportion of subjects who never experience PGA ≥ 2 throughout the study.
- Time to first worsening (PGA ≥ 2), defined as days from date of Visit 1 date to the date of first occurrence of PGA ≥ 2 . Subjects who never experience PGA ≥ 2 throughout the study will be censored at the date of their last PGA assessment.

For subjects entering the study with a PGA score ≥ 1 :

- Proportions of subjects who achieve PGA = 0 at least 1 time during the study

• [REDACTED]

• [REDACTED]

[REDACTED]

For subjects entering the study with a PGA score ≥ 2 :

- Proportions of subjects who achieved PGA = 0 or 1 at least 1 time during the study.
- Proportions of subjects who never achieve PGA = 0 or 1 throughout the study.

The following endpoints will be summarized over subjects in ITT population:

- Duration (days) of treatment episodes, defined as time (days) from the date of each PGA ≥ 2 (or PGA ≥ 1 for the first episode) to 1 day before each subsequent treatment success (PGA = 0). The date of the last PGA assessment will be used as the end date for episodes ongoing at the end of the study.

- [REDACTED]
- [REDACTED] \geq [REDACTED]
- [REDACTED]
- [REDACTED]
- [REDACTED]
- [REDACTED] change and percent change from baseline in %BSA affected by visit (OC and LOCF).
- [REDACTED] change and percent change from baseline in PASI score by visit (OC and LOCF)
- [REDACTED] \geq [REDACTED]
- [REDACTED] \geq [REDACTED]
- [REDACTED] \geq [REDACTED]

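### Read literally, the SAP's compliance rule labels subjects who enter clear and never have a treatment episode as non-compliant, although no dose was due

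*SAP*

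**What the plan says.** **Who gets drug.** Under Protocol 3.1 and SAP 3, subjects entering at PGA 0 stop treatment and are observed; treatment resumes if PGA reaches 2 or more. Protocol 5.1.5.3 says the same: "Subjects with a PGA of 0 will not receive treatment" unless they worsen to that level.

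**What counts as exposure.** SAP 11.4 uses "Total expected number of days exposed, calculated as the sum of number of days over all treatment episodes". SAP 11.7 defines the episodes: "Duration (days) of treatment episodes, defined as time (days) from the date of each PGA" of 2 or more (1 or more for the first episode), ending the day before PGA 0 is reached. An episode still open at the end of the study closes at the last PGA assessment.

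**How compliance is computed.** "Percent compliance will be calculated as the total number of doses administered within treatment episodes over the total expected number of days exposed". For a period with an unreturned diary or a missing dosing record, "the number of doses taken during that period is assumed to be 0".

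**How subjects are flagged.** A subject is compliant at 80% or more "compliance over the entire duration of study". The fallback follows directly: "If the percentage of study medication compliance is unknown, the subject is assumed to be non-compliant with study medication". SAP 11.4 makes an exception for subjects without diaries in the grams-per-dose average. It makes none, for the compliance flag, for subjects without a treatment episode.

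**Population.** SAP 7 defines one analysis set, all enrolled subjects, and states: "All efficacy and safety analysis will be performed over ITT analysis set".

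**The concern.** The trial studies intermittent use, and time off drug after clearing is a result it sets out to describe. SAP 11.7 has an endpoint for subjects who enter clear and never worsen to PGA 2 or more, so the plan expects some subjects to need no drug. Such a subject had no dose to miss, yet the compliance flag offers only two outcomes, and the fallback leads to non-compliant.

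At stake is the meaning of one row in the exposure table. The share compliant would mix adherence among subjects who were due to apply drug with the frequency of needing none. Because the table is also split by pivotal-study treatment group, two groups with the same adherence could show different compliance merely because different numbers entered clear and had no episode.

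**Working it through.** The plan states no figure to reproduce. The check applies the SAP 11.4 rule as written, then sizes the effect.

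**Step 1: the rule case by case.** Percent = 100 × doses ÷ expected days. The flag is non-compliant if the percentage is below 80% or unknown. The day counts are illustrative.

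| Subject | Doses | Expected days | Percent | Flag |
|---|---|---|---|---|
| Enters at PGA 0, no episode | 0 | 0 | undefined | non-compliant, by the fallback |
| Treated, no diary returned | 0 | 100 | 0% | non-compliant, by the threshold |
| Treated, 90 doses recorded | 90 | 100 | 90% | compliant |
| Enters at PGA 0, drifts to PGA 1 only, if that opens a first episode | 0 | 200 | 0% | non-compliant, by the threshold |

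Row 2 shows that the fallback is not needed for lost diaries: the numerator is set to 0, so the percentage is known. The fallback can act only where expected days are 0 or cannot be derived, for example when PGA is missing.

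Row 4 is a separate route to the same label. SAP 11.7 lets the first episode start at PGA 1 or more and does not limit this to subjects who enter at that level. Under SAP 3 and Protocol 5.1.5.3, a subject who entered clear gets drug only at PGA 2 or more. If the first-episode wording is applied to that subject, days with no dose due become expected days.

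**Step 2: size.** Let c be the share compliant among subjects with at least 1 expected day, and f the share of enrolled subjects with none.

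- Share compliant among those with expected days: c
- Share reported if the others are kept in and flagged non-compliant: c × (1 − f)

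Planned enrolment is 850 (SAP 6). The documents give neither f nor c. Assume 5% to 20% enter clear and 10% to 50% of those never have an episode:

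- Low: f = 0.05 × 0.10 = 0.005; 850 × 0.005 = 4.25, about 4 subjects
- High: f = 0.20 × 0.50 = 0.10; 850 × 0.10 = 85 subjects

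| Assumed c | f = 0.5% | f = 10% |
|---|---|---|
| 90% | 0.90 × 0.995 = 89.55% | 0.90 × 0.90 = 81.0% |
| 80% | 0.80 × 0.995 = 79.6% | 0.80 × 0.90 = 72.0% |

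**Step 3: between groups.** With the same c in both pivotal-study groups, the spurious difference is c × (f₁ − f₂). If one group sat at each end of the assumed range, it would be 0.90 × (0.10 − 0.005) = 0.0855, or 8.55 percentage points. That is the limit of the assumed range, not an estimate.

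**The case against.** The best defence is that an undefined ratio is not an unknown one. Both terms are known to be 0, so the percentage is not applicable, and the SAP nowhere says that such a case counts as unknown. Other text points the same way. SAP 11.4 introduces these summaries as taken across the span of treatment episodes, and a subject without an episode has no such span. SAP 10.1 lets each percentage use the denominator that suits its purpose. The population sentence in SAP 7 speaks of efficacy and safety analyses, and SAP 11.4, unlike 11.3, 11.8 and 11.11, does not name the ITT set. SAP 11.1 also counts subjects who apply any study medication, so those who apply none can be identified.

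Part of this stands. Non-compliant is the literal outcome of the rule, not something the SAP says in words about these subjects, and a careful programmer might leave them out. But none of these lines excludes them, while the specific rule in 11.4 offers no third category. Two programmers could produce different tables from the same text.

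It also stands that the consequence is limited. There is no compliance-based analysis set, no statistical testing (SAP 10.1), and no use of the flag in the visible endpoints of SAP 11.7 or the subgroups of 11.8.

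A reader might go further and infer that subjects from the tapinarof arms will look less adherent than those from vehicle. The documents do not give PGA at entry by group, or how many in each group never have an episode, so the direction is not established. Nor can every subject with no episode be called a durable responder: some may enter clear and leave early, and SAP 6 anticipates high discontinuation.

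**Conclusion.** The point holds as a defect in a descriptive summary. Taken literally, SAP 11.4 classifies subjects with no treatment episode as non-compliant, and because missing diary data are already set to 0 doses, these are the main subjects its fallback reaches. The reported share compliant is too low by c × f: 0.45 points (0.90 × 0.005) to 9.0 points (0.90 × 0.10) when c = 90%. That range rests on assumed values of f and c, and on reading an undefined percentage as unknown. A spurious difference between pivotal-study groups follows if f differs between them; its sign and size cannot be known from the documents. Efficacy and safety results are not touched.

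**What to change.** In SAP 11.4:

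1. Compute percent compliance and the 80% flag only for subjects with at least 1 expected day of treatment.
2. Report subjects with 0 expected days in a separate row, *no treatment episode / not applicable*, with counts overall and by pivotal-study group.
3. Limit the non-compliant default to subjects whose expected days cannot be derived. Missing diaries need no such default, because they already count as 0 doses.

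In SAP 11.7, reconcile the first-episode threshold of PGA 1 or more with the treatment-start rules for subjects entering at PGA 0 in SAP 3 and Protocol 5.1.5.3, so that days on which no drug was due are not counted as expected days. Without this, step 1 would not help a subject in row 4 of the table above.

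The cost is a sentence or two of SAP text, one table row and a small programming change. No new data are needed.

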11.5 Prior and Concomitant Medications

Prior (within 30 days before Visit 1 and with stop dates prior to Visit 1) medications would have been captured in the pivotal studies and will not be presented in this study.

Concomitant (ongoing or with stop dates on or after Visit 1) medications will be listed by subject. If the medication is ongoing or the stop year is missing, the medication will be considered as received for the entire duration of the study. Concomitant medications that are ongoing as of the end of the pivotal studies will be displayed in a separate listing.

Medications will be coded using WHO-DD terminology. Concomitant medications will be summarized by WHO-DD Anatomical-Therapeutic-Chemical (ATC) classification and preferred term (PT), overall and by DB treatment group.

11.6 Medical History and Concurrent Procedures

Medical history (including previous and ongoing medical conditions) collected during the pivotal studies will be coded using MedDRA and listed by subject. Medical history will be summarized by system organ class (SOC) and PT, overall and by DB treatment group.

11.7 Efficacy Endpoints

Efficacy endpoints are as follows:

For subjects entering the study with a PGA score of clear (0):

- Proportion of subjects who experience PGA ≥ 2 at least 1 time during the study.
- Proportion of subjects who never experience PGA ≥ 2 throughout the study.
- Time to first worsening (PGA ≥ 2), defined as days from date of Visit 1 date to the date of first occurrence of PGA ≥ 2 . Subjects who never experience PGA ≥ 2 throughout the study will be censored at the date of their last PGA assessment.

For subjects entering the study with a PGA score ≥ 1 :

- Proportions of subjects who achieve PGA = 0 at least 1 time during the study

• [REDACTED]

• [REDACTED]

[REDACTED]

For subjects entering the study with a PGA score ≥ 2 :

- Proportions of subjects who achieved PGA = 0 or 1 at least 1 time during the study.
- Proportions of subjects who never achieve PGA = 0 or 1 throughout the study.

The following endpoints will be summarized over subjects in ITT population:

- Duration (days) of treatment episodes, defined as time (days) from the date of each PGA ≥ 2 (or PGA ≥ 1 for the first episode) to 1 day before each subsequent treatment success (PGA = 0). The date of the last PGA assessment will be used as the end date for episodes ongoing at the end of the study.

- [REDACTED]
- [REDACTED] \geq [REDACTED]
- [REDACTED]
- [REDACTED]
- [REDACTED]
- [REDACTED] change and percent change from baseline in %BSA affected by visit (OC and LOCF).
- [REDACTED] change and percent change from baseline in PASI score by visit (OC and LOCF)
- [REDACTED] \geq [REDACTED]
- [REDACTED] \geq [REDACTED]
- [REDACTED] \geq [REDACTED]

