7.4. Follow-up Visit

Subjects will return to the study site 4 weeks (± 3 days) after last treatment to complete follow-up assessments as follows:

- Brief physical exam
- Vital signs measurements
- Urine pregnancy test (females of CBP)
- Blood sample collection for clinical laboratory tests (serum chemistry, hematology, diagnostic tests)
- Urinalysis
- Photography of a representative area of the subject's disease area (optional for subjects; at a subset of study centers)
- PGA score
- BSA affected calculation
- PASI
- DLQI
- AE recording
- Concomitant medication recording

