A subject is considered to have completed the study when he/she completes all required procedures/visits for the 40-week (Visit 11) treatment period. The end of the study is defined as when the last active subject has completed the Follow-up Visit.

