10. DATA CONVENTIONS FOR ANALYSIS

10.1 General Statistical Principles

The study efficacy and safety results will be summarized descriptively. There will be no statistical testing.

All observed and derived variables (e.g., change from baseline, percentage change from baseline, and response status) that are summarized will be presented in by-subject listings. Unless otherwise noted, the data will be sorted by DB treatment group and subject number and then by date within subject number.

For categorical parameters, the number and percentage of subjects in each category will be presented. The denominators for percentages will be the number of subjects appropriate for the purpose. For continuous parameters, descriptive statistics will include number of subjects, mean, standard deviation (SD), median, minimum, and maximum.

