11.8 Efficacy Analyses

All efficacy parameters will be summarized over the ITT analysis set overall and by DB treatment group. Summaries of efficacy endpoints by visit will be performed using OC and LOCF methods.

Time to event parameters, such as the time from treatment success to subsequent worsening (PGA ≥ 2) or duration of treatment episode, will be summarized by the Kaplan-Meier product limit method using OC. Median time to event will be estimated. If the median time is not determined, other percentiles will be estimated.

The remaining efficacy endpoints will be summarized descriptively as follows: continuous data will include the mean, SD, minimum, maximum, median, and number of observations; descriptive summary statistics for categorical data will include frequency counts and percentages.

For the following efficacy outcomes:

1. Proportions of subjects who achieve PGA = 0 at least 1 time during the study (for subjects entering the study with a PGA score ≥ 1):
2. Proportions of subjects who experienced PGA ≥ 2 at least 1 time during the study (for subjects entering the study with a PGA score = 0):
3. PGA scores at Week 40 (LOCF)
4. BSA [REDACTED] change from baseline to Week 40 (LOCF)
5. PASI [REDACTED] change from baseline to Week 40 (LOCF)

subgroup analyses will be generated for the following groupings:

- Baseline PGA
- Age (<65 and ≥ 65 years old)
- Sex
- Race (White, Other)
- Baseline % BSA affected – ($<10\%$, $\geq 10\%$)
- Duration of disease (<5 years, 5-10 years, >10 years)
- Country (USA and Canada)

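### For subjects entering at PGA 0, the crude *ever* and *never* PGA ≥2 percentages carry no follow-up condition, so *never* probably mixes durable response with early exit

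*SAP*

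**What the plan says.** For subjects entering at PGA 0, SAP 11.7 lists three endpoints: the proportion with at least one PGA ≥2, the "Proportion of subjects who never experience PGA ≥ 2 throughout the study", and time to first worsening. The rule for the third is "Subjects who never experience PGA ≥ 2 throughout the study will be censored at the date of their last PGA assessment".

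SAP 11.8 analyses time-to-event endpoints by KM over the ITT set, overall and by double-blind treatment group. Its commitment on output is "Median time to event will be estimated. If the median time is not determined, other percentiles will be estimated". The remaining categorical endpoints get counts and percentages. Subgroup outcome 2 is "Proportions of subjects who experienced PGA ≥ 2 at least 1 time during the study", restricted to PGA-0 entrants. Time to worsening is not among the five subgroup outcomes.

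On denominators, SAP 10.1 says only "The denominators for percentages will be the number of subjects appropriate for the purpose". The observed-case and LOCF rules in SAP 8 concern by-visit summaries.

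On the window, SAP 3 says "A subject is considered to have completed the study when he/she completes all required procedures/visits for the 40-week (Visit 11) treatment period" and also "The end of the study is defined as when the last active subject has completed the Follow-up Visit". Protocol 7.4 has subjects return "after last treatment to complete follow-up assessments as follows", and the list that follows includes the PGA.

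SAP 6 anticipates high discontinuation, with about 300 of 850 subjects completing. That figure is study-wide.

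**The concern.** Subjects who enter clear stop treatment and are observed for how long the response lasts, so a *never* percentage will be read as a durability result. The only text that touches incomplete follow-up is the censoring sentence, which applies the *never* label to anyone without a recorded PGA ≥2, whenever the last PGA falls. If the percentages follow that label over the ITT set, a subject who leaves clear at Week 4 counts the same as one who stays clear to Week 40.

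Two things follow. First, over a fixed window, dropout can only push crude *never* up and crude *ever* down compared with complete follow-up over that same window. Second, double-blind groups or subgroups with the same worsening rate but different dropout will show different percentages. The second effect matters most in the subgroup tables, where the crude *ever* proportion has no listed KM counterpart.

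**Working it through.** **The plan's own figures.** 300/850 = 35.3% retained, so 550/850 = 64.7% do not complete. The sample size rests on ICH E1 exposure and not on a power formula. No expected value is given for either proportion, so there is no further figure to reproduce.

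**Assumptions, not in the documents.** The true probability of worsening by Week 40 is p = 0.5, 0.7 or 0.9 (true *never* 50, 30 or 10%). The worsening hazard is constant. Dropout is constant and independent of worsening. The fraction retained at Week 40 is r = 300/850, 0.80 or 1. The study-wide 300/850 is borrowed for PGA-0 entrants, for whom no figure is given.

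**Formulas.**
- λ = −ln(1−p)/40 and δ = −ln(r)/40.
- Crude *ever* to Week 40 = λ/(λ+δ) × (1 − exp(−40(λ+δ))); crude *never* = 1 − crude *ever*.
- Completed Week 40 without worsening = r(1−p). Left earlier without worsening = crude *never* − r(1−p).

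**Worked case, p = 0.7, r = 300/850.** 40λ = 1.204 and 40δ = 1.041, so 40(λ+δ) = 2.245. Crude *ever* = (1.204/2.245) × (1 − 0.106) = 0.479, and crude *never* = 0.521. Of that, 0.3 × 0.353 = 0.106 completed and 0.521 − 0.106 = 0.415 left earlier.

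**Worked case, p = 0.7, r = 0.80.** Crude *never* = 0.359, of which 0.240 completed and 0.119 left earlier.

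| True *never* at Week 40 | Crude, 65% dropout | Crude, 20% dropout | Crude, no dropout |
|---|---|---|---|
| 50% | 67.1% | 54.6% | 50% |
| 30% | 52.1% | 35.9% | 30% |
| 10% | 33.6% | 16.1% | 10% |

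**Timing of dropout.** If all 65% leave at Week 36 instead, crude *never* = exp(−36λ) − r(exp(−36λ) − exp(−40λ)). For a true 30% this is 0.338 − 0.353 × 0.038 = 0.325. Late dropout therefore does little harm.

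**Week-44 scores.** If these count and all completers attend, subtract r(1−p)(1 − exp(−4λ)). For a true 40-week 30%, crude *never* becomes 0.509 at 65% dropout (0.521 − 0.012) and 0.266 with no dropout (0.300 − 0.034). The comparison has to be made within one window.

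**Where to read the KM curve.** The Week-40 visit is Day 40×7+1 = 281, ±3, so Days 278 to 284. A simulation with 4-weekly visits spread evenly over ±3 days, against a true *never* of 50/30/10%, gave:

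| KM rule | No dropout | 65% dropout |
|---|---|---|
| Read at Day 284, Week-44 PGA excluded | 44/25/7% | 43/23/6% |
| Read at Day 284, Week-44 PGA kept | 50/30/10% | 48/28/9% |
| Nominal visits, read at Week 40 | 50/30/10% | 50/30/10% |

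The first rule understates *never* by about 3 to 7 points. Subjects seen unworsened early in the visit window are censored there, and later events in the window fall on a shrunken risk set.

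**The case against.** **No rule classes leavers as *never*.** The censoring sentence belongs to the time-to-event endpoint, and SAP 10.1 leaves denominators open. This stands as a limit on certainty: the classification is the natural reading of an ITT percentage, not a written rule. If another rule was meant, it still needs stating.

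**Kaplan-Meier is already planned for the same subjects.** It is, overall and by double-blind group, and Protocol 10.4.2 pairs *ever* with the median time. SAP 11.1 adds withdrawal counts and KM curves of days in study, though not for PGA-0 entrants. This answers most of the problem. What remains is the lack of a specified Week-40 probability and of a subgroup counterpart.

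**The endpoint is an observed count in a descriptive study without testing.** True, and no inference is affected. But the percentages are then the result, and readers will take *never* as durability.

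**Worsening at exit will be seen.** The Early Termination visit scores PGA, and unscheduled visits are available for suspected worsening. These would catch some events at exit but none afterwards. SAP 10.5 keeps unscheduled visits out of table summaries and does not say whether that applies here.

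**The window is clear enough.** Largely so. Wording that covers the whole study and the last PGA points to including the Follow-up Visit; Week 40 defines only subject completion. One sentence would settle it.

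**The split may already be planned.** The table outline in SAP 15 has no content in the public text, so it cannot be said that no table shows it. By-subject listings would in any case allow it to be rebuilt.

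**Conclusion.** The point holds as a cheap improvement, minor to should-fix. The two crude proportions and the *ever* subgroup table have no follow-up condition and, on the natural reading, combine durable response with early exit. Under constant hazards and independent dropout, a true 40-week *never* of 30% reads about 52% at 65% dropout, with roughly four-fifths of that group (41.5 of 52.1) having left early. At 20% dropout it reads about 36%. These sizes are illustrative: the worsening rates are assumed and the 65% is study-wide.

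The documents do not support three stronger readings that a reader might infer:
- That the SAP states that leavers count as *never*. It does not; this is inferred.
- That the durability evidence as a whole is compromised. The planned KM analysis handles dropout if censoring is non-informative.
- That crude *never* always exceeds the 40-week value. That direction is assured only against full follow-up over the same window. With Week-44 scores counted and little dropout, it can fall below.

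**What to change.** 1. In the main and subgroup tables, split the crude result for PGA-0 entrants into three: worsened; completed Week 40 without PGA ≥2; left earlier without PGA ≥2. This needs no censoring assumption.
2. From the KM analysis already planned, report the probability of PGA ≥2 by Week 40 and its complement, with 95% CI and number at risk, overall and by double-blind group. Add subgroups only where numbers allow.
3. State one window for both the proportions and the KM analysis. Either keep Week-44 PGA in the KM follow-up, as the current wording already implies, and read at the end of the Week-40 window; or run KM on nominal visits and read at Week 40. Do not read at Day 284 with calendar-day censoring and Week-44 PGA excluded. Say how unscheduled and Early Termination PGA scores enter.
4. State that the KM figure assumes non-informative censoring.

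Cost: SAP wording, some extra output and no new data. The *never* figure will probably look less favourable. Late and subgroup KM estimates may be imprecise: for a true *never* of 30%, only about 11% of PGA-0 entrants would reach Week 40 unworsened and still in follow-up at 65% dropout, and 24% at 20% dropout.
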